6.0 PRODUCT DESCRIPTION

6.1 General

The Noxsano Bandage (study device) uses an electrochemical reaction to generate highly controlled doses of NO for wound healing. The electrochemical reaction reduces sodium nitrite (meat tenderizer) to NO. To achieve this efficiently, an electrochemical mediator is used that 'shuttles' electrons from the anode to the nitrite. The dressing has a battery, two electrodes, electrical connectors, and a hydrogel formulation containing the sodium nitrite and electrochemical mediator. Each component is described in Figure 2 (section 1.3.1) above.

6.3 Packaging

The Noxsano Bandage is assembled by Noxsano, Inc., autoclave sterilized and supplied to OhioHealth Research Institute (OHRI). The hydrogel formulation in the dressing is 'activated' by soaking the device in 25-50 ml (depending on dressing size) of sterile water for 5 minutes. This process 'connects' the electrodes and initiates the electrochemical generation of NO. NO delivery continues until the dressing is removed (3-5 days). The dressing delivers $0.8-1.2 \times 10^{-7}$ moles of NO per minute to the wound continuously during use. This level of NO mimics the level the body would generate during normal wound healing. The dressing will be packaged in a sterile container and delivered in-person by the manufacturer (staff from Noxsano, Inc.) to OHRI.

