5.0 STUDY PROCEDURES AND ASSESSMENTS

5.1 Schedule of Events

Group 1 (Healthy Volunteers):

The initial healthy volunteer safety study will last a total of 4.5 weeks. Healthy volunteers will have the study device applied for 3 consecutive days (up to 72 hours), followed by weekly visits for 4 weeks of observation for tolerance, side effects, and adverse reactions. Weekly visits will occur every 7 ± 2 days after the Day 3 visit.

Assessment	Screening (via phone)	Baseline	tion: Day 0Study Device	3 ± 0 days Treatment:	$y 7 \pm 2 \text{ days}^4 \text{ Follow-Up}$:	Unscheduled Visit
Informed Consent		X				
Medical history	X					
Concomitant medications	X	X	X	X	X	X
OhioHealth Research Institute Clinic Visit (Research Only)		X				
Critical Limb Care Center (Riverside Methodist Hospital Wound Center) visit (research-only)			X	X	X	
Shaving of left posterior calf		X				
Photograph			X	\mathbf{x}^5	X	
Noxsano Bandage application			X			
SAR Questionnaire			X	X	X	

Group 2 (Wound Care Subjects):

The wound care subject treatment period will consist of twice per week study device applications to a specific ulceration for up to the first 4 weeks of treatment and then weekly re-application thereafter. When deemed permissible by the clinical judgment of the principal or sub-investigator or when 4 weeks is reached, re-application of the study device will change to weekly. This weekly re-application will occur until the wound is healed, or for up to 12 weeks (whichever occurs first). For subjects that do not exhibit any reduction in wound size at 2 months, application will stop and standard treatment protocols will be pursued.

At the conclusion of the treatment period (maximum of 3 months), subjects will be followed every 3 months for 12 consecutive months for observation of late side effects or adverse reactions (up to 3 months of active treatment, 12 months of follow-up observation, 15 months maximum).

IRB# 1331496 Page 24 Version 6.0

⁴ Day 10, 17, 24, and 31

⁵ Photograph and compensation are given on Day 3 only during Treatment Period

Assessment	Screening / Baseline	Day OInitial Study Device	ery 3 ± 2 days ⁶ Treatment:	$2 \text{ try } 7 \pm 2 \text{ days}^7 \text{ Treatment:}$	$imo \pm 14 days^8 Follow-Up$:	Unscheduled Visit
Informed Consent	X					
Routine medical history / physical exam	X					X
Concomitant medications	X	X	X	X	X	X
HgbA1c (subjects with diabetes)	X					
ABI (subjects with arterial insufficiency)	X					

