5.3 Photographs

Photographs of the study device application site and wounds (Group 2) will be taken using a digital camera, an FDA Class 1 510(k) exempt medical device. Digital photographs are routinely taken in the OhioHealth Riverside Methodist Hospital Critical Limb Care Center, therefore, their equipment will be utilized for the study.

Group 1(Healthy Volunteers): A photograph will be taken on Day 0 of the shaved area on the left posterior calf prior to study device placement. A photograph of the site where the study device was applied will also be taken on Day 3, following removal of the study device, and at each follow-up visit (Days 10, 17, 24, and 31). All photographs will be

IRB# 1331496 Page 25 Version 6.0

⁶ Weeks 1-4, 2 times per week study device changes or until change to weekly is permitted by investigator.

⁷ Weeks 5-12, weekly study device changes until wound has healed or 3 months is reached.

^{83, 6, 9,} and 12 months post-treatment

uploaded into the study electronic case report forms (eCRFs) by a member of the study staff.

Group 2 (Wound Care Subjects): Photographs of the wound with a conventional ruler in place will be obtained at baseline, Day 0 (Initial Device Application), treatment, and follow-up visits. Photographs will be taken by a wound care nurse and uploaded in the study eCRFs by a member of the study staff.

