5.8 Treatment Visits and Assessments

IRB# 1331496 Page 27 Version 6.0

Group 1 (Healthy Volunteers): Healthy volunteers will be seen in the Critical Limb Care Center on Day 0 for Application (± 0 days) and Day 3 for Removal (± 0 days) during the study treatment period. Subjects will be instructed to call the Critical Limb Care Center [contact]) during regular business hours (0700-1600), and the Study Investigators will be available after-hours [contact] for [name], [contact] for [name], [contact] for [name])for concerns regarding adverse reactions or other general questions. Contact numbers for the study investigators will be provided in the informed consent document. The following evaluations and processes will be completed and data recorded in the REDCap eCRF:

- ♦ SAR Questionnaire (App. A)
- ♦ Concomitant medications
- ♦ Photograph (Day 3 only after the removal of the study device)

Group 2 (Wound Care Subjects): Subjects will be seen in the Critical Limb Care Center twice a week (every 3 days \pm 2 days) for up to 4 weeks. Clinical judgment of the principal or investigator will permit a subject to discontinue twice weekly bandage changes prior to the end of 4 weeks. After the first 4 weeks of treatment or when deemed permissible by the investigator, subjects will be seen in the Critical Limb Care Center weekly (7 days \pm 2 days) for a total treatment period of up to 3 months. The following evaluations will be completed and data recorded in the REDCap eCRF:

- ♦ Study device application
- ♦ Photograph of the study device application site (on Day 0 prior to study device application; following the removal of the old device and prior to application of the new device on subsequent treatment visits)
- ♦ Wound measurements
- ♦ Percent granulation tissue
- ♦ SAR Questionnaire (App. A)
- ♦ Concomitant medications

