5.10 Unscheduled Visits

A critical limb wound care podiatrist will be on call at all times.

Subjects will be instructed to call the Critical Limb Care Center [contact]) during regular business hours (0700-1600), and the Study Investigators will be available afterhours [contact] for [name], [contact] for [name], [contact] for [name]) for concerns regarding adverse reactions or other general questions. Subjects will be seen on an urgent basis as-needed based on podiatrist recommendation during regular business hours at the Critical Limb Care Center.

Unscheduled visits are additional visits that occur at times other than the protocol predetermined required visits during study participation. If an unscheduled visit occurs, the following will be collected from the subject's medical record and entered in the REDCap eCRF:

- ♦ Routine physical examination by a podiatrist, including assessment of the lower extremities
- ♦ Concomitant medications
- ♦ Photograph of the study device application site
- ♦ Wound Measurements
- ♦ Percent granulation tissue
- ♦ Bandage re-application if necessary
- ♦ SAR Questionnaire (App. A)

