5.11 Subject Withdrawal or Discontinuation

Subjects have the right to withdraw from the study at any time and for any reason without penalty or loss of benefits to which the subject is otherwise entitled. If a subject decides to withdraw, all study assessments, tests, and procedures will be stopped. An exit interview will be requested to understand why the subject chose to withdraw. The subject will also be offered the option to have data collection from the electronic medical record to continue in order to track wound progression. The Investigators may withdraw the subject at any time to protect the health, safety, or welfare of the subject. At the last point of contact, the date and reason for discontinuation will be documented, and every effort should be made to follow-up the status of any ongoing adverse events prior to withdrawal.

[figure not shown]
Subjects that do not present for the initial Noxsano Bandage application appointment will be withdrawn from the study and replaced.

Study participation may continue per the Schedule of Events (section 5.1) until one of the following criteria applies:

Group 1:

♦ Unacceptable adverse reactions warranting discontinuation of treatment in the opinion of the Investigators: Subjects experiencing any allergic reaction or infection at the device application site will be removed from study treatment.

IRB# 1331496 Page 29 Version 6.0

Group 2:

- ♦ Unacceptable adverse reactions warranting discontinuation of treatment in the opinion of the Investigators: Subjects experiencing any allergic reaction or infection at the device application site will be removed from study treatment.
- ♦ *Missed weekly treatment visits and discontinuation from study treatment*: Weekly treatment visits will be indicated as "missed" if the deviation from the planned date is > 2 days (i.e., 3 or 7 days ± 2 days, during the 3 month study period). If a subject misses 2 consecutive treatment visits, they will be removed from study and not replaced.

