7.0 SAFETY REPORTING

7.1 Definitions

7.1.1 Adverse Event

An **adverse event** (AE) is any unfavorable or unintended event, physical or psychological, associated with a research study, which causes harm or injury to a research participant as a result of the participant's involvement in a research study. The event can include abnormal laboratory findings, symptoms, or disease associated with the research study. The event does not necessarily have to have a causal relationship with the research, any risk associated with the research, the research intervention, or the research assessments.

Adverse events may be the result of the interventions and interactions used in the research; the collection of identifiable private information in the research; an underlying disease, disorder, or condition of the subject; and/or other circumstances unrelated to the research or any underlying disease, disorder, or condition of the subject.

[figure not shown]
Subjects will be followed in terms of tolerance/side effects/adverse reactions:

- ♦ **Tolerance**: pruritus (itchy skin), dermatitis (dry skin), pain
- ♦ **Side effects**: erythema (red skin), edema (swollen skin), pressure ulcer (skin breakdown), melanogenesis (skin darkening), hyperemia (increased local blood flow)
- ♦ **Adverse reactions**: any systemic side effect, including (but not limited to) fever, nausea, vomiting, or hypotension (low blood pressure)

Group 1 healthy volunteers are not dysfunctional in the generation of NO due to chronic wound healing, and therefore their endothelium will contain 'normal levels.' As such, use of the Bandage will represent an increase above physiologically normal levels in the endothelium of the healthy volunteers. In contrast, Group 2 subjects have chronic wounds that are known to be dysregulated in NO. In this instance, the treatment returns their endothelium to physiologically normal levels of NO (see section 1.3.5).

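### Section 6.3 has one device removed at 3-5 days, but the Group 2 weekly phase plans 5-9 days; the protocol body states no Group 2 maximum wear time and no device rule for a missed visit

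*Combined protocol and SAP*

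**What the plan says.** **Product description.** Section 6.3: "NO delivery continues until the dressing is removed (3-5 days". The same section gives a flux of 0.8-1.2 × 10⁻⁷ moles per minute throughout use.

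**Schedule.** Sections 5.1 and 5.8 plan Group 2 changes every 3 ± 2 days for up to 4 weeks, then every 7 ± 2 days. Section 5.1: "This weekly re-application will occur until the wound is healed, or for up to 12 weeks (whichever occurs first". Footnote 7 to its schedule table: "Weeks 5-12, weekly study device changes until wound has healed or 3 months is reached". The weekly phase can start sooner. Section 5.8: "Clinical judgment of the principal or investigator will permit a subject to discontinue twice weekly bandage changes prior to the end of 4 weeks". Section 5.8 also places removal of the old device and application of the new one at the same visit.

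**Missed and unscheduled visits.** Section 5.11 counts a treatment visit as missed "if the deviation from the planned date is > 2 days", and then: "If a subject misses 2 consecutive treatment visits, they will be removed from study and not replaced". Section 5.10 lists "Bandage re-application if necessary" among the items for an unscheduled visit, without linking it to a missed visit or a day limit. Section 5.12 covers contact attempts, and section 6.5 covers training; neither gives a wear limit.

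**Wear described before Group 2.** Section 1.3.5 reports wear by the founders for up to 72 hours, and section 5.7 sets the same limit for Group 1. Section 1.3.1 reports pig dressings changed every 3-4 days.

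**Device and known effects.** Section 1.3.1 gives a thickness of 1 cm at the ends and 2 cm at the battery. Section 7.1.1 lists "pressure ulcer (skin breakdown" among the side effects to be followed.

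**The concern.** The figure in 6.3 and the weekly schedule meet only at day 5. The nominal 7-day interval, the default for 8 of the 12 treatment weeks, lies outside the 3-5 days that 6.3 describes. Group 1 has an explicit ceiling on wear and Group 2 does not. Because 5.11 tolerates one missed visit and says nothing about the device, a powered device 1-2 cm thick could remain over a diabetic or ischemic ulcer well beyond even the weekly interval.

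Two things are at stake. The first is safety: the site is photographed and measured once the old device is off, so the skin beneath it is not seen on schedule while the device stays in place. The second is treatment delivery: section 1.3.3 makes the benefit depend on continuous, controlled delivery, so the protocol should state that one device performs for as long as it is scheduled to be worn.

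**Working it through.** No sample size, power or error rate is involved; the check is arithmetic on intervals and windows.

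**Inputs.** Removal at 3-5 days (6.3). Change intervals of 3 ± 2 and 7 ± 2 days (5.1, 5.8, 5.11). Removal from study only after 2 consecutive misses (5.11). Twelve weeks of treatment, weekly from week 5 by default (5.1, footnote 7). Ten Group 2 subjects (3.2). Since the change is made at the visit, wear time equals the interval between attended visits.

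**1. Wear per device, window counted from the last change**

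| Situation | Calculation | Days on one device |
|---|---|---|
| Twice-weekly phase | 3 − 2 to 3 + 2 | 1-5 |
| Weekly phase | 7 − 2 to 7 + 2 | 5-9 |
| One weekly visit missed, no unscheduled change | 14 − 2 to 14 + 2 | 12-16 |

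The upper end of the twice-weekly phase reproduces the 5 days in 6.3. The weekly phase exceeds it by 7 − 5 = 2 days nominally and 9 − 5 = 4 days at the edge of the window (9/5 = 1.8 times). One missed weekly visit gives 12/5 = 2.4 to 16/5 = 3.2 times.

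**2. Sensitivity: window counted from fixed planned dates.** Section 5.11 speaks of a planned date, so this reading is possible. One visit can then be 2 days early and the next attended visit 2 days late. Longest interval with both weekly visits attended: (14 + 2) − (7 − 2) = 11 days. Longest with one missed between them: (21 + 2) − (7 − 2) = 18 days.

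**3. Experience with one device.** In people it is 72 hours, or 3 days. In pigs it is 3-4 days between changes, repeated over weeks. The pig work therefore bears on weeks of nitric oxide exposure through successive devices, not on 9 days under a single one.

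**4. How often a missed-visit rule would apply.** With the switch at week 4 there are 8 × 10 = 80 weekly intervals. If every subject switched at the very start, there would be about 12 × 10 = 120. The documents give no miss rate. At an assumed 5-10% per visit, that is 80 × 0.05 = 4 to 120 × 0.10 = 12 missed weekly visits in the whole study.

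**5. Time off the device.** If it is removed at day 9 and not replaced, the gap until the next attended visit is 12 − 9 = 3 to 16 − 9 = 7 days.

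**The case against.** **The missing rule may exist elsewhere.** Appendix G goes to every subject and covers troubleshooting and safety reporting. It, the consent forms and the section 10 addendum were not available, and any of them could hold a wear limit or a missed-visit instruction. This stands, and the conclusion is confined to the protocol body for that reason. It does not remove the mismatch between 6.3 and 5.1/5.8.

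**The 3-5 days is descriptive.** It is a parenthesis in a packaging paragraph, and sections 2.2, 3.3, 5.1 and 5.8 agree on weekly changes. That also stands: rewording 6.3 alone would be nearly clerical. A reader might infer that the device stops working after day 5. The documents do not support that, since 6.3 says delivery lasts until removal.

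**The 72-hour comparison.** A reader might set 5-9 days against 72 hours and call weekly wear 1.7-3.0 times a safety limit (5/3 and 9/3). Sections 1.3.5 and 7.1.1 tie the Group 1 limit to excess nitric oxide in healthy skin, not to device life or pressure. The 72 hours shows how far human experience reaches; it is not a threshold that Group 2 breaches.

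**Hidden skin reactions.** Section 7.1.1 expects symptoms within 24-72 hours, so one might say a reaction lies unseen for 5 − 3 = 2 to 9 − 1 = 8 days. That restarts the onset clock with every device. By default, weekly wear follows four weeks of twice-weekly removal, photographs and questionnaires. Plantar wounds are excluded, and a podiatrist is on call at all times. These reduce the risk. The on-call route still depends on the subject noticing a problem under a covering device.

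**Conclusion.** The point holds in a limited form. Section 6.3 does not match the weekly schedule: planned wear is 5-9 days, or up to 11 on the fixed-date reading, against 3-5 days described. The protocol body sets no Group 2 maximum and leaves the device unaddressed after one missed visit, so wear could reach 12-16 days (18 on the fixed-date reading). The longer figures assume that the device stays in place and that no unscheduled visit takes place. The described single-device experience, 72 hours in people and 3-4 days in pigs, does not cover 9 days.

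This is a gap in instructions with a safety side, not a finding of under-dosing, overexposure or harm. The mismatch does not depend on the assumed miss rate. Whether the missing instruction is missing from the whole plan depends on documents not available here. It is a cheap improvement of modest priority.

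**What to change.** 1. **Section 6.3.** Obtain from the manufacturer the in-use duration supported for one device at the stated flux, and replace the 3-5 days with text that matches the weekly schedule. If the supported figure is 7 or 8 days, shorten the upper side of the change window to 7 −2/+0 or 7 −2/+1, leaving the 5.11 definition of a missed visit unchanged for removal from study. A figure below 7 days would put the visit schedule itself in question, which is a larger change than this one.
2. **Section 5.8.** State a maximum wear time for one device: the supported figure, no longer than 9 days, counted from the last change.
3. **Section 5.11, matched in Appendix G.** When a treatment visit is not attended, the device is changed at an unscheduled visit under 5.10, or removed and replaced with a standard dressing, before the maximum is reached. Contact should start on the planned day, because a weekly visit is labelled missed only once it is more than 2 days late, which is after day 9.

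**Cost.** One manufacturer figure, one corrected line and two short rules; no scheduled visits are added. At the assumed miss rate, expect about 4-12 unscheduled changes or removals across the study. A subject whose device is removed at day 9 without a new one loses 3-7 days of treatment. If the site counts windows from fixed dates, a 9-day cap would also affect some attended visits up to 11 days apart, so 5.8 should say that the window runs from the last change.

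**Limit.** The fix bounds wear after a missed visit. It does not shorten the scheduled 5-9 days between inspections, unless the manufacturer's figure narrows the window.

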6.4 Intended Population

The Noxsano Bandage is intended for use in patients with chronic and non-healing wounds.

6.5 Product Training Requirements

Investigators, wound care practitioners, and research staff will be trained by Noxsano, Inc. staff in an onsite in-service at the Critical Limb Care Center at OhioHealth Riverside Methodist Hospital on the usage of the Noxsano Bandage, including, but not limited to the following:

- ♦ Clinical aspects of packaging, handling, application, and mechanism of action of the Noxsano Bandage;
- ♦ "Troubleshooting" the Noxsano Bandage, including device malfunctions and frequently asked questions;
- ♦ Reporting and advising on patient safety issues, side effects, and adverse reactions.

6.6 Product Receipt and Tracking

IRB# 1331496 Page 32 Version 6.0

The study device will be delivered in-person by the manufacturer (staff from Noxsano, Inc.) and stored in a secure area at the offices of OHRI or in a locked storage room accessible only to OHRI staff at the OhioHealth Riverside Methodist Hospital Critical Limb Care Center.

Study device receipt will be tracked by research staff at each delivery using Device Tracking Logs (App H).

6.7 Product Storage and Accountability

The device will be labeled and stored in a secure area at the offices of OHRI or in a locked storage room accessible only to OHRI staff at the OhioHealth Riverside Methodist Hospital Critical Limb Care Center. Device storage and accountability will be controlled only by the assigned, trained research staff at the site. Each device will be labeled with the following:

- ♦ Company name
- ♦ Company contact information
- ♦ Device identification number
- ♦ Date of sterilization
- ♦ Shelf life (6 months)

[figure not shown]
Study device usage and administration will be tracked by research staff at each subject visit using Device Tracking Logs (App H). Per the manufacturer, there are no special storage requirements (shelf-stable at room temperature).

6.8 Product Return or Destruction

Any unused or expired product will be retrieved in-person by the manufacturer (staff from Noxsano, Inc.) upon study closure.

Study device return will be tracked by research staff at the conclusion of study enrollment using Device Tracking Logs (App. H).

IRB# 1331496 Page 33 Version 6.0

7.0 SAFETY REPORTING

7.1 Definitions

7.1.1 Adverse Event

An **adverse event** (AE) is any unfavorable or unintended event, physical or psychological, associated with a research study, which causes harm or injury to a research participant as a result of the participant's involvement in a research study. The event can include abnormal laboratory findings, symptoms, or disease associated with the research study. The event does not necessarily have to have a causal relationship with the research, any risk associated with the research, the research intervention, or the research assessments.

Adverse events may be the result of the interventions and interactions used in the research; the collection of identifiable private information in the research; an underlying disease, disorder, or condition of the subject; and/or other circumstances unrelated to the research or any underlying disease, disorder, or condition of the subject.

[figure not shown]
Subjects will be followed in terms of tolerance/side effects/adverse reactions:

- ♦ **Tolerance**: pruritus (itchy skin), dermatitis (dry skin), pain
- ♦ **Side effects**: erythema (red skin), edema (swollen skin), pressure ulcer (skin breakdown), melanogenesis (skin darkening), hyperemia (increased local blood flow)
- ♦ **Adverse reactions**: any systemic side effect, including (but not limited to) fever, nausea, vomiting, or hypotension (low blood pressure)

Group 1 healthy volunteers are not dysfunctional in the generation of NO due to chronic wound healing, and therefore their endothelium will contain 'normal levels.' As such, use of the Bandage will represent an increase above physiologically normal levels in the endothelium of the healthy volunteers. In contrast, Group 2 subjects have chronic wounds that are known to be dysregulated in NO. In this instance, the treatment returns their endothelium to physiologically normal levels of NO (see section 1.3.5).

Therefore, Group 1 healthy volunteers are more likely to experience adverse events related to hypersensitivity and skin reactions, and are thus being limited to 3 days (up to 72) hours of Bandage wear. It is anticipated that symptoms will manifest within 24-72 hours of application and resolve within 7-10 days of removal, but could take as long as 30 days or more depending on individual skin regeneration. Regarding Group 2 wound care subjects, we expect manifestation and resolution of symptoms on the same timeline, but cannot state decisively as this is the first study in this population. Finally, as itching is a normal consequence of wound healing, we expect this to occur in the majority of Group 2 subjects. No preclinical evidence of significant risk has been demonstrated with the Noxsano Bandage, and therefore is not anticipated or expected during this study.

IRB# 1331496 Page 34 Version 6.0

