3.3 Expected Study Duration and Subject Participation

Group 1: The initial healthy volunteer safety study will last a total of 4.5 weeks. Healthy volunteers will wear the study device for 3 consecutive days (up to 72 hours), followed by weekly visits for 4 weeks of observation for tolerance, side effects, and/or adverse reactions.

For the purposes of this study, if 2 subjects experience an unacceptable adverse reaction warranting discontinuation of treatment in the opinion of the Investigators during the initial healthy volunteer phase, the study will be halted and Group 2 (and the remainder of the initial phase, if applicable) will not be completed. Allergic reactions and infections at the study device application site will be considered unacceptable at any clinical severity; other adverse reactions will be deemed "unacceptable" by the Investigators on a case-by-case basis dependent upon clinical severity (App. A).

Group 2: The wound care subjects will have twice per week study device applications to a specific ulceration for up to the first 4 weeks of treatment and then weekly reapplication thereafter. For subjects that exhibit any reduction in wound surface area, this application will occur until the wound is healed, or for up to 3 months (whichever occurs first). For subjects that do not exhibit any reduction in wound size at 2 months, application will stop and standard treatment protocols will be pursued. At the conclusion of the treatment window (up to 3 months), subjects will be followed every 3 months for 12 consecutive months for observation of late side effects or adverse reactions (3 months of active treatment, 12 months of follow-up observation, 15 months total).

IRB# 1331496 Page 19 Version 6.0

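### After final device removal, Group 2 has no scheduled safety assessment until the 3-month visit, and subjects discontinued for lack of healing have none at all, although the protocol expects reactions to resolve well before then

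*Combined protocol and SAP*

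**What the plan says.** **Expected course of reactions.** Section 7.1.1 expects symptoms to appear 24-72 hours after application and to clear 7-10 days after removal, but adds that this "could take as long as 30 days or more depending on individual skin regeneration". For Group 2 it says "we expect manifestation and resolution of symptoms on the same timeline", while admitting that this cannot be stated firmly in a population not studied before.

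**Group 1 schedule.** The device is removed on Day 3. Section 5.1 states "Weekly visits will occur every 7 ± 2 days after the Day 3 visit", and its footnote gives "Day 10, 17, 24, and 31". The SAR questionnaire is given at each of these visits. Under Section 3.2, Group 1 follow-up is completed and assessed before Group 2 starts.

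**Group 2 schedule.** The SAR is given at every treatment visit, twice weekly and later weekly. Once treatment ends, the footnote to the Group 2 table in Section 5.1 places the visits at 3, 6, 9 "and 12 months post-treatment"; the table and Section 5.9 give a window of 14 days either side.

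**Early stopping.** Section 5.11 ends study follow-up for Group 2 subjects with no decrease in wound area at 2 months, or with less than a 50% decrease at 3 months. It takes subjects with an allergic reaction or infection at the site off study treatment, but lists this among the points up to which study participation may continue. Section 5.13 speaks of subjects who discontinue participation because of such reactions.

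**Open events.** Section 7.2.3 allows ongoing as a recorded outcome and asks for the date when an event has resolved. Section 5.11 asks, at the last contact, that "every effort should be made to follow-up the status of any ongoing adverse events prior to withdrawal". Section 7.3.1 covers updates to reported events under the heading of serious adverse events.

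**The concern.** How long reactions last after removal is a basic result of a first-in-human device study. The protocol states what it expects, so its visits can be compared with that expectation. Group 2 wears the device for up to 3 months, against up to 72 hours in Group 1, and it is the group in which the protocol is least sure of the course. Yet it is the group with no scheduled look during the period when resolution is expected.

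What is at stake is the timing of resolution in Group 2 and, for subjects discontinued for lack of healing, any scheduled safety information after removal. With 10 subjects in the group, losing this for even a few leaves little to report.

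**Working it through.** This is calendar arithmetic. No power or error-rate figure is involved.

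**1. Reproduce the Group 1 schedule.** Removal is Day 3 and visits follow every 7 days, so visit day = 3 + 7k for k = 1 to 4. This gives Days 10, 17, 24 and 31, as stated. 31 / 7 = 4.43 weeks, consistent with the stated 4.5.

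**2. Group 1, days after removal** (visit day minus 3, window ± 2 days):

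| Visit | Days after removal | With window |
|---|---|---|
| Day 10 | 7 | 5-9 |
| Day 17 | 14 | 12-16 |
| Day 24 | 21 | 19-23 |
| Day 31 | 28 | 26-30 |

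The first two visits bracket the expected 7-10 days. The last falls at 28 days, or at most 30. If the ± 2 days is read as running from visit to visit, the last could be as late as 4 × 9 = 36 days. Only the tail is uncovered.

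**3. Group 2, first scheduled SAR after final removal.** The length of 3 months in days is an assumption. Section 5.11 equates it with 12 weeks, or 84 days; a calendar quarter is about 91 days.

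- At 84 days: 84 - 14 = 70 and 84 + 14 = 98.
- At 91 days: 91 - 14 = 77 and 91 + 14 = 105.
- Overall range: 70-105 days.

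Scheduled assessments at 7-10 days: 0. At about 30 days: 0. The first look comes at least 70 - 30 = 40 days, and up to 105 - 30 = 75 days, after the 30-day mark. A reaction present at final removal and gone at the 3-month visit has therefore resolved at some unobserved point within 70-105 days, unless the subject recalls the date or came in unscheduled.

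**4. Group 2 subjects discontinued for lack of healing.** Section 5.11 ends their study follow-up. Scheduled assessments after removal: 0.

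**5. Subjects stopped for a reaction.** The wording can be read either way:

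- Section 5.11 removes them from study treatment. That differs from its wording for missed treatment visits (removed from study) and for non-healers (study follow-up ended), which suggests that their visits continue.
- The sentence introducing that list in Section 5.11, and the payment rule in Section 5.13, describe the reaction as the end of study participation, which suggests that their visits do not continue.

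**6. Rule for open events.** Section 5.11 asks for effort up to withdrawal, and Section 7.3.1 covers updates for serious events. No visible text requires a non-serious event open at the last scheduled visit to be followed further.

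**The case against.** The case against has weight.

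- **Group 1 largely fits.** Its visits cover the expected 7-10 days. The stated tail is open-ended, so no fixed schedule could cover it. A reader might infer that Group 1 follow-up is too short for its purpose; the documents do not support that. What remains is the absence of a rule for a reaction still open at Day 31.
- **Resolution can still be recorded.** The Group 2 3-month visit includes the SAR, a photograph and wound measurements. A reader might infer that Group 2 reactions are never seen to resolve. Where that visit takes place, only the date is lost.
- **Other cover exists.** Reactions during treatment are checked at every treatment visit. A podiatrist is on call, unscheduled visits collect the SAR, and Group 2 subjects are patients of the same center. Section 7.3 requires all adverse events observed or reported after consent to be recorded, with no stated end. This lowers the risk of missing a troublesome reaction, but it relies on the subject calling or on routine care and does not schedule an assessment.
- **The decision to open Group 2 is not undermined.** A reader might infer that it is. The halting rule in Sections 2.1 and 3.3 counts subjects with unacceptable reactions and does not depend on time to resolution.
- **Subjects stopped for a reaction.** A reader might infer that they lose their remaining visits. The text is ambiguous and does not say so.

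None of this supplies a scheduled Group 2 assessment in the expected period, or any assessment after removal for discontinued non-healers.

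**Conclusion.** The point holds for Group 2 and, narrowly, for Group 1 events open at the last visit. By the protocol's own timeline, Group 2 has no scheduled safety assessment in the period when reactions should resolve. The first comes about 70-105 days after final removal, and subjects discontinued for lack of healing have none. Whether subjects stopped for a reaction stay under observation needs to be settled in the text.

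This is a worthwhile and inexpensive correction; it does not invalidate the study. It rests on taking 3 months as 84-91 days and on the visible text. The Section 10.0 addendum and the SAR form were not available for review. The addendum might contain follow-up wording, so the absence of a general rule is stated only for what can be read. The documents give no rate of slow-resolving reactions, so the number of subjects affected cannot be estimated.

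**What to change.** 1. **Sections 5.1 and 5.9:** add one telephone SAR about 30 days after final device removal for all Group 2 subjects. A reaction gone by the call is then dated to within about 30 days rather than 70-105, and the subject is asked for the date while recall is fresh.
2. **Section 5.11:** state that this call also applies to subjects discontinued for lack of healing or stopped for a reaction. The present text ends study follow-up for the non-healers, so the call would contradict it unless both are amended together.
3. **Section 7.2.3:** state that any device-related event still open at the last scheduled visit, in either group, is followed by telephone until resolved or stable, with the date recorded. Say whether events rated possibly related under Section 7.2.2 are included.
4. **Sections 5.11 and 5.13:** reconcile the wording on whether safety follow-up continues after treatment is stopped.

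The cost is a protocol amendment and a few calls by existing staff with the existing questionnaire: one per subject in a group of 10, plus any open events. The last-subject date may move slightly if an event stays open.
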